2.8.4 Other safety data

2.8.4.1 ECG and cardiac imaging data

Not applicable

2.8.4.2 Vital signs

Vital signs will include blood pressure and pulse rate measurements.

All vital signs data will be listed by treatment group, patient, and visit, and if ranges are available, abnormalities will be flagged. Abnormal values are marked in [Section 5.4](#). All data, including data from unscheduled visits, will be considered when identifying abnormal values. Analysis of the vital sign measurements using summary statistics for the change from Baseline for each post-Baseline visit, minimum post-Baseline value and maximum post-Baseline value will be performed. These descriptive summaries will be presented by vital sign and treatment group. Change from Baseline will only be summarized for subjects with both Baseline and post-Baseline values.

The number and percentage of subjects with newly occurring or worsening notable values, including notable changes from Baseline, will be summarized by vital sign parameter, scheduled post-Baseline visit and treatment group. Subjects with any newly occurring or worsening value meeting the clinically notable criteria will be counted under the applicable

criteria. For a subject to meet the criterion of a newly clinically notable occurrence, the subject needs to have a Baseline value which does not meet the criteria for categorizing a value as notable. For a subject to meet the criterion of a worsening occurrence, the subject needs to have a Baseline value which is clinically notable and also have a worse post-Baseline value. For subjects with a missing value at Baseline, post-Baseline values meeting the notable criterion will be considered as newly occurring. For subjects with both Baseline and post-Baseline values which are clinically notable but in opposing directions (e.g. Low at Baseline and high at post-Baseline, or vice versa), the post-Baseline notable value will be considered as newly occurring.

2.9 Pharmacokinetic endpoints

Not applicable.

2.10 PD and PK/PD analyses

Not applicable.

2.11 Patient-reported outcomes

See [Section 2.7.1](#).

2.12 Biomarkers

Not applicable.

2.13 Other Exploratory analyses

Not applicable.

3 Sample size calculation

The sample size was calculated based on the primary efficacy variable ASAS40 response at Week 24 for the FAS. Available data from the DESIR cohort ([Molto et al 2014](#)) and the DANBIO registry ([Glintborg et al 2017](#)) showed an ASAS40 response of 30% in TNF α inhibitor naïve axSpA subjects, that were treated with common *biological* DMARDs.

Data from MEASURE 2/MEASURE 3 trials ([Sieper et al 2017](#), [Pavelka et al 2017](#)) showed an ASAS40 response of 43.2% and 43.9% at Week 16, while approximately 50% of subjects did not achieve an ASDAS clinically important improvement (defined as change from BSL of ≥ 1.1) criterion at Week 12. Taking into account the longer duration of active treatment with secukinumab 150 mg and the substantial proportion of subjects that will be escalated to 300 mg, it is justifiable to conservatively assume an ASAS40 response of 50% at Week 24.

With an ASAS40 response of 50% for the secukinumab 150 mg/300 mg arm and a 30% response in the SOC arm at Week 24 (corresponding to an OR of 2.3), 134 subjects per treatment arm are required to achieve a power of 90% to demonstrate superiority at a significance level of 0.05 using the 2-group continuity corrected χ^2 test of equal proportions.

In order to account for some uncertainties in the underlying assumptions and to compensate for some expected dropout and protocol violations, a total of 300 subjects (150 patients in the T2T and 150 patients in the SOC arm) should be randomized into this study.

4 Change to protocol specified analyses

Not applicable.

5 Appendix

5.1 Imputation rules

5.1.1 Study drug

The following rules should be used for the imputation of the dose end date for a given study treatment component:

Scenario 1

If the dose end date is completely missing and there is no end of treatment (EOT) page and no death date, the patient is considered as on-going.

The patient should be treated as on-going and the cut-off date should be used as the last dosing date.

Scenario 2

If the dose end date is completely or partially missing and the EOT page is available:

- Case 1: The dose end date is completely missing and the EOT completion date is complete, then this latter date should be used.
- Case 2: Only year (YYYY) of the dose end date is available and YYYY < the year of EOT date, then use 31DECYYYY.
- Case 3: Only year (YYYY) of the dose end date is available and YYYY = the year of EOT date, then use EOT date.
- Case 4: Both year (YYYY) and month (MMM) are available for dose end date and YYYY = the year of EOT date and MMM < the month of EOT date, then use last day of the Month (MMM).

All other cases should be considered as a data issue and the statistician should contact the data manager of the study.

After imputation, compare the imputed date with start date of treatment.

If the imputed date is < start date of treatment, then use the treatment start date.

Otherwise, use the imputed date.

Patients with missing start dates are to be considered missing for all study treatment component related calculations and no imputation will be made. If start date is missing then end-date should not be imputed.

5.1.2 AE date imputation

The following table explains the notation used in the logic matrix. Please note that **missing start dates** will not be imputed.

	Day	Month	Year
Partial Adverse Event Start Date	Not used	MON	YYYY
Treatment Start Date (TRTSTD)	Not used	TRTM	TRTY

	NON MISSING	MON < TRTM	MON = TRTM	MON > TRTM
YYYY MISSING	NC Uncertain	NC Uncertain	NC Uncertain	NC Uncertain
YYYY < TRTY	(D) Before Treatment Start	(C) Before Treatment Start	(C) Before Treatment Start	(C) Before Treatment Start
YYYY = TRTY	(B) Uncertain	(C) Before Treatment Start	(A) Uncertain	(A) After Treatment Start
YYYY > TRTY	(E) After Treatment Start	(A) After Treatment Start	(A) After Treatment Start	(A) After Treatment Start

The following table is the legend to the logic matrix.

If AE end date is complete and AE end date < Treatment start date or AE end date is partial and AE imputed end date < Treatment start date, then AE start reference = min (informed consent date, earliest visit date from SV) Else if AE end date is partial,AE end date > = Treatment start date or AE is ongoing , then AE start reference = treatment start date.

Relationship	Time imputation
Before AE start reference	Partial date indicates AE start date prior to AE start reference
After AE start reference	Partial date indicates AE start date after AE start reference
Uncertain	Partial date insufficient to determine relationship of AE start date to AE start reference
Imputation Calculation	
NC/Blank	No convention
(A)	MAX(01MONYYYY, AE start reference+1 day)

Relationship	Time imputation
(B)	AE start reference+1
(C)	15MONYYYY
(D)	01JULYYYY
(E)	01JANYYYY
Complete date	No date imputation

If time is captured for the study
Case1: if AE start date is not equal to AE start reference then do the following:
 If minutes missing then AESTMF = M and time is imputed to hh:00
 If minutes missing then AESTMF = H and time is imputed to 00:00
Case2: if AE start date = AE start reference then AESTMF = H and time is imputed to treatment start time + 1 hour

Adverse Event End Date Imputation

Imputed date = date part of original date, if complete date.

Imputed date = min (completion/discontinuation visit date, DEC 31, date of death), if month is missing.

Imputed date = min (completion/discontinuation visit date, last day of the month, date of death), if day is missing.

Adverse Event End Time Imputation

If the AE end date is complete and time is captured in the study then:

Case 1. If AE end date is not equal to Treatment end date, then do the following:

If minutes missing then time is imputed to hh:00 if time missing then time is imputed to 00:00.

Case 2. If AE end date = Treatment end date then time is imputed to treatment end time.

If the AE end date is partial then end time is imputed to 00:00.

Imputed Date Flag

If year of the imputed date is not equal to YYYY then date flag = Y

else if month of the imputed date is not equal to MON then date flag = M

else if day of the imputed date is not equal to day of original date then date_flag = D

else date flag = null

Imputed Time Flag

If hours of the imputed time is not equal to hours of original time then time flag = H

else if minutes of the imputed time is not equal to minutes of original time then time flag = M
else time flag = null.

5.1.3 Concomitant medication date imputation

This algorithm is used when event is the partial start date of the concomitant medication.

The following table explains the notation used in the logic matrix. Please note that missing start dates will not be imputed.

		Day	Month	Year
Partial CM Start Date		Not used	MON	YYYY
Treatment Start	TRTSDT	Not used	TRTM	TRTY

The following matrix explains the logic behind the imputation.

	MON MISSING	MON < TRTM	MON = TRTM	MON > TRTM
YYYY MISSING	(C2) Uncertain	(C1) Uncertain	(C1) Uncertain	(C1) Uncertain
YYYY < TRTY	(D) Before Treatment Start	(A) Before Treatment Start	(A) Before Treatment Start	(A) Before Treatment Start
YYYY = TRTY	(C2) Uncertain	(A) Before Treatment Start	(C1) Uncertain	(B) After Treatment Start
YYYY > TRTY	(E) After Treatment Start	(B) After Treatment Start	(B) After Treatment Start	(B) After Treatment Start

The following table is the legend to the logic matrix.

Relationship	
Before Treatment Start	Partial date indicates CMD start date prior to Treatment Start Date
After Treatment Start	Partial date indicates CMD start date after Treatment Start Date
Uncertain	Partial date insufficient to determine relationship of CMD start date relative to Treatment Start Date
Imputation Calculation	
(A)	15MONYYYY
(B)	01MONYYYY

(C1 or C2)	IF relative reference start = ELSE IF relative reference start = TRTSDT+1 ' THEN	before treatment start	THENTRSDT-1
(D)	01JULYYYY		
(E)	01JANYYYY		

Concomitant Medication End Date Imputation

If not ongoing then:

Imputed date = date part of CMENDTC, [if complete date](#)

Imputed date = min(completion/discontinuation visit date, DEC 31) , if month is missing, [\(C2, D, E\)](#)

Imputed date = min(completion/discontinuation visit date, last day of the Month) , if day is missing. [\(A, B, C1\)](#)

Concomitant Medication Date Flag

If not a complete date then

Y - If year of the imputed date is not equal to YYYY else M – If month of the imputed date is not equal to MON else D.

5.1.3.1 Prior therapies date imputation

Same methodology as in [Section 5.1.3.](#)

5.1.3.2 Post therapies date imputation

Same methodology as in [Section 5.1.3.](#)

5.1.3.3 Other imputations

Same methodology as in [Section 5.1.3.](#)

5.2 AEs coding/grading

AEs are coded using the MedDRA terminology. The latest MedDRA version will be used and will be described in the footnote of relevant outputs.

AEs will be assessed according to the Common Terminology Criteria for Adverse Events (CTCAE) version 4.03.

The CTCAE represents a comprehensive grading system for reporting the acute and late effects of cancer treatments. CTCAE grading is by definition a 5-point scale generally corresponding to mild, moderate, severe, life threatening, and death. This grading system inherently places a value on the importance of an event, although there is not necessarily proportionality among grades (a grade 2 is not necessarily twice as bad as a grade 1). The CTCAE grade of 5 (death)

is not used; rather, “fatal” is collected as AE outcome and death information is also collected on a separate eCRF page.

5.3 Concomitant medication grouping

The following concomitant medications will be categorized by the classes below.

- 1. Nonsteroidal anti-inflammatory drugs (NSAIDs):** Celecoxib, diclofenac, ibuprofen, etoricoxib, meloxicam, naproxen, indometacin, parecoxib, acemetacin, aceclofenac, piroxicam, dexketoprofen, nabumetone, rofecoxib, lornoxicam, diclofenac sodium, ketoprofen, flurbiprofen, piroxicam betadex, sulindac, naproxen sodium, niflumic acid, tenoxicam.

2. Other axSpA medication(s):

Analgesics		
A) Non-opioid	B) Opioid	(C) Other
Metamizole, metamizole sodium, naloxone hydrochloride, caffeine, papaver somniferum latex, paracetamol, paracetamol, flupirtine maleate, flupirtine maleate	Naloxone hydrochloride; tilidine hydrochloride, codeine, morphine sulfate, codeine phosphate, oxycodone, tramadol, tramadol hydrochloride	Tizanidine hydrochloride, amitriptyline hydrochloride, methocarbamol, amitriptyline, pregabalin, citalopram, methocarbamol

3. DMARDs:

ts DMARDs	cs DMARDs		
JAKi	SS	MTX	Other
Upadacitinib	Sulfasalazine	Methotrexate sodium	Leflunomide

4. Biological DMARDs:

(A) aIL-17	(B) TNFi	(C) Other
Secukinumab, ixekizumab	Golimumab, adalimumab, etanercept, certolizumab pegol, infliximab, adalimumab biosimilar	Ustekinumab

5. Glucocorticoids:

(A) Systemic steroids (oral, iv, im)	(B) Intraarticular steroids
Prednisolone, cortisone acetate, prednisone, triamcinolone, dexamethasone, prednisolone acetate, cortisone	Cortisone acetate, triamcinolone, prednisolone acetate, triamcinolone hexacetonide

5.4 Laboratory parameters derivations

The table below shows all laboratory parameters that will be presented.

Table 5-1 Laboratory Tests

Order	Laboratory Group Subgroups	Tests [SI unit]
1	Hematology Red Blood Cells	Hematocrit [%] Hemoglobin [mmol/L] Platelet count [10E9/L] Red cell count [10E12/L]
	White Blood Cell Count and Differential	Basophils [%] Eosinophils [%] Lymphocytes [%] Monocytes [%] Neutrophils [%]
		Absolute Basophils [10E9/L] Absolute Eosinophils [10E9/L] Absolute Lymphocytes [10E9/L] Absolute Monocytes [10E9/L]
2	Clinical Chemistry	Creatinine [umol/L] Blood urea [mmol/L] Albumin [g/L] Alkaline Phosphatase [U/L] Total Bilirubin [umol/L] Total protein [g/L]
	Lipids	Cholesterol HDL [mmol/L] Cholesterol LDL [mmol/L] Triglycerides [mmol/L]
3	Urinalysis	Glucose WBC Occult Blood Protein

The following criteria will be used to define expanded limits and notable abnormalities of key laboratory tests.

Hematology variables:

- Hemoglobin: ≥ 20 g/L decrease from Baseline

- Platelet count: < lower limit of normal (LLN)
- White blood cell count: $< 0.8 \times \text{LLN}$
- Neutrophils: $< 0.9 \times \text{LLN}$
- Eosinophils: $> 1.1 \times \text{ULN}$
- Lymphocytes: $> 1.1 \times \text{ULN}$

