Neutropenia was more frequently observed with secukinumab than with placebo, but most cases were mild, transient, and spontaneously reversible.

The incidence of hypersensitivity AEs was slightly higher with secukinumab compared with placebo, with the difference mostly due to mild to moderate urticaria and eczema not associated with systemic symptoms.

The incidence of selected rare events of interest (major adverse cardiovascular events and malignancies) adjusted for exposure over 52 weeks was comparable to placebo in clinical trials across multiple indications.

There was no clear association between treatment with secukinumab and new onset of inflammatory bowel disease but due to the potential involvement of the interleukin-17 (IL-17) pathway in the pathogenesis of the disease, it is not possible to rule out a potential increased risk of exacerbation.

Secukinumab 300 mg was comparable to 150 mg and both doses showed comparable safety to placebo and etanercept over 52 weeks of treatment.

Infections, neutropenia, and hypersensitivity are important identified risks, while malignancies, major adverse cardiovascular events, immunogenicity, Crohn's disease, and hepatitis B reactivation are important potential risks. Interaction with live vaccines is an important potential interaction (and also included as an important potential risk).

No new identified risks were reported. During the reporting interval, a Risk Management Plan (RMP) update was triggered upon request from Pharmacovigilance Risk Assessment Committee, to include suicidal ideation and behavior (SIB) as an important potential risk in the RMP on the basis that "although causality has not been established, SIB meets the criteria as important potential risk because a potential biological mechanism cannot be completely ruled out since the biological role of IL-17 receptor ligands is still largely unknown, and consideration of the potential public health impact". The RMP is currently being updated for this change. At its completion SIB will be listed as an important potential risk in the RMP.

No new safety signal was identified and no actions were taken for safety reasons during the reporting period of the latest drug safety update report.

The risk to patients in this trial will be minimized by compliance with the eligibility criteria, close clinical monitoring, and extensive guidance to the investigators, provided in the current version of the Investigator's Brochure (IB).

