16.1 Appendix 1: Clinically notable laboratory values

The following criteria will be used to define expanded limits and notable abnormalities of key laboratory tests.

Clinically notable values will be forwarded to Novartis/CRO at the same time that they are sent to investigators. Any action based on these laboratory values should be discussed with Novartis/CRO personnel.

Table 16-1 Safety analyses: expanded limits and notable criteria

Laboratory Variable	Final Harmonization	
	Notable Criteria	SI Units
	Standard Units	
LIVER FUNCTION AND RELATED VARIABLES		
SGOT (AST)	> 3 x ULN	> 3 x ULN
SGPT (ALT)	> 3 x ULN	> 3 x ULN
GGT		
Bilirubin	> 2 x ULN	> 2 x ULN
Alkaline phosphatase	> 2.5 x ULN	> 2.5 x ULN
RENAL FUNCTION, METABOLIC AND ELECTROLYTE VARIABLES		
Creatinine (serum)	> 2 x ULN	> 2 x ULN

16.2 Appendix 2: Assessment of spondyloarthritis international society criteria for axial spondyloarthritis

ASAS criteria for classification of axSpA will be applied as defined by [Sieper et al \(2009\)](#).

Diagnosis of axial spondyloarthritis according to the assessment of spondyloarthritis international society classification criteria

Diagnosis of axSpA (either AS or nr-axSpA) according to ASAS axSpA classification criteria to be applied in patients with back pain for at least 3 months and age of onset < 45 years:

- Sacroiliitis on imaging with ≥ 1 SpA feature **or**
- HLA-B27 positive with ≥ 2 SpA features

Sacroiliitis on imaging

- Active (acute) inflammation on MRI highly suggestive of sacroiliitis associated with SpA (see [Appendix 6](#))
- Definite radiographic sacroiliitis according to the modified New York diagnostic criteria (van der Linden et al 1984) (see [Appendix 5](#))

Spondyloarthritis features

- Inflammatory back pain
- Arthritis
- Enthesitis (heel)
- Uveitis
- Dactylitis
- Psoriasis
- Crohn's disease or colitis
- Good response to NSAIDs
- Family history for SpA
- HLA-B27
- Elevated CRP

Source: Sieper J, Rudwaleit M, Baraliakos X, et al (2009) The Assessment of SpondyloArthritis international Society (ASAS) handbook: a guide to assess spondyloarthritis. Ann Rheum Dis.; 68 Suppl 2:ii1-44

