2.8.3 Laboratory data

All laboratory data will be listed with abnormal values flagged.

Laboratory data measured more than 30 days after the last dose of study drug is regarded as post-treatment and will not be summarized or analyzed, only listed.

The below laboratory parameter data will be analyzed.

Hematology: Hemoglobin, hematocrit, platelet count, red blood cell, WBC and differential WBC counts.

Clinical chemistry: glucose, urea, creatinine, total bilirubin, AST, ALT, gamma-glutamyl transferase (GGT), alkaline phosphatase, sodium, potassium, bicarbonate, calcium, phosphorous, total protein, albumin, and uric acid.

Lipid panel: High density lipoprotein, low density lipoprotein, cholesterol and triglycerides must be measured from a fasting blood sample.

Urinalysis: Protein, glucose, blood and WBCs.

For all continuous laboratory parameters, summary statistics for absolute and change from Baseline values will be provided at each visit. All laboratory data (including any unscheduled assessments) will be listed with abnormal values flagged.

For categorical urinalysis laboratory parameters (Glucose, Occult Blood, Protein), a frequency table of results will be produced by laboratory parameter, scheduled visit and treatment.

Shift tables for laboratory parameters will be provided in order to compare a subject's Baseline value to the value at each study visit, relative to the normal reference range for each lab parameter. Abnormal values marked in Section 5.4 will be used to evaluate whether a particular laboratory test value for each visit is normal, low or high relative to the Baseline value also categorized as normal, low or high. These summaries will be presented by laboratory parameter, visit and treatment group.

In addition, shift tables relative to the normal reference ranges will be used to summarize the change from Baseline to the most extreme post-Baseline for each laboratory parameter. For each laboratory test, the subjects will be classified into one of the four mutually exclusive groups (low, normal, high, and low + high), defined as follows:

- Low: at least one post-Baseline value below the normal range and none above the normal range
- High: at least one post-Baseline value above the normal range and none below the normal range
- Normal: all the post-Baseline values within the normal range
- Low + High: at least one post-Baseline value below the normal range and at least one above the normal range

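### SAP 5.4 conflicts with SAP 2.8.3 on which laboratory tests are presented, and it defines no notable-value count for any of the five liver and renal limits in protocol Table 16-1

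*SAP*

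**What the plan says.** Four places bear on which laboratory tests are reported and which values count as notable.

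- **SAP 2.8.3 (Laboratory data)** names the tests to be analysed. The haematology list includes white cells with differential. The chemistry list runs to 16 tests and includes "total bilirubin, AST, ALT, gamma-glutamyl transferase (GGT), alkaline phosphatase". The section promises by-visit summary statistics for continuous parameters, shift tables by visit and to the most extreme value, and listings with abnormal values flagged.
- **SAP 5.4 (Laboratory parameters derivations)** states of Table 5-1: "The table below shows all laboratory parameters that will be presented". Below the table it adds: "The following criteria will be used to define expanded limits and notable abnormalities of key laboratory tests". Six criteria follow, all under a haematology heading: haemoglobin, platelets, white cells, neutrophils, eosinophils and lymphocytes.
- **Protocol Appendix 1, Table 16-1**, whose caption says it is for safety analyses, has a block headed "LIVER FUNCTION AND RELATED VARIABLES" and a renal block. Together they give limits for AST, ALT, bilirubin, alkaline phosphatase and creatinine. Protocol 8.4.4 refers to this appendix for the definition of notable findings.
- **SAP 2.1.2** says that a summary of notable laboratory values will use the most extreme post-Baseline measurement. **SAP section 4**, on changes to protocol-specified analyses, reads as not applicable.

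**The concern.** The SAP gives two different answers to the question of which tests are reported. A programmer who takes Table 5-1 as the full list would leave out tests that one working from SAP 2.8.3 would include.

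The notable criteria raise a separate problem. SAP 5.4 uses much the same introduction as the protocol appendix but lists none of the appendix's limits. The planned summary of notable values, run on the SAP's stated criteria, would therefore contain no liver or renal line. Showing the overall safety and tolerability of secukinumab is a secondary objective, and a count of patients above a stated multiple of ULN is a basic display for these enzymes and for creatinine.

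The neutrophil measure is also unclear. Protocol 4.4 states that "Infections, neutropenia, and hypersensitivity are important identified risks", and SAP 5.4 gives a neutrophil limit, but the table shows neutrophils only as a percentage.

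**Working it through.** No sample-size or error-rate arithmetic applies. The check sets the lists side by side.

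**Step 1. Chemistry.**
- SAP 2.8.3 lists 16: glucose, urea, creatinine, total bilirubin, AST, ALT, GGT, alkaline phosphatase, sodium, potassium, bicarbonate, calcium, phosphorous, total protein, albumin and uric acid. Protocol 8.4.4.2 collects the same 16.
- Table 5-1 lists 6: creatinine, urea, albumin, alkaline phosphatase, total bilirubin and total protein.
- Absent: 16 − 6 = 10, namely glucose, AST, ALT, GGT, sodium, potassium, bicarbonate, calcium, phosphorous and uric acid.

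**Step 2. Lipids.** SAP 2.8.3 lists 4 and Table 5-1 lists 3 (HDL, LDL, triglycerides). Absent: 4 − 3 = 1, total cholesterol.

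**Step 3. White cells.** The total count appears only in the subgroup title, "White Blood Cell Count and Differential", with no row and unit of its own. The percentages shown are "Basophils [%] Eosinophils [%] Lymphocytes [%] Monocytes [%] Neutrophils". The absolute counts shown are basophils, eosinophils, lymphocytes and monocytes, so absolute neutrophils have no row.

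**Step 4. Total for Table 5-1.** Chemistry and lipids give 10 + 1 = 11 absent tests. The two white-cell rows would make 11 + 2 = 13, but those two are less certain (see the objection).

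**Step 5. Notable limits.**

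| Test | Protocol Table 16-1 | Limit in SAP 5.4 | Row in Table 5-1 |
|---|---|---|---|
| AST | > 3 x ULN | none | no |
| ALT | > 3 x ULN | none | no |
| Bilirubin | > 2 x ULN | none | yes |
| Alkaline phosphatase | > 2.5 x ULN | none | yes |
| Creatinine | > 2 x ULN | none | yes |

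The SAP carries 0 of the 5 limits. GGT has a row in the protocol table but no limit, so there was none to carry over. None of the six SAP haematology criteria appears in protocol Table 16-1.

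**Step 6. Do the other outputs fill the gap?** The shift tables in SAP 2.8.3 class a value as low, normal or high against the reference range. An ALT of 1.1 x ULN and one of 5 x ULN both fall in the high class, although 1.1 < 3 < 5 and only the second exceeds the protocol's limit. The number of patients above the limit cannot be read from a shift table. By-visit means and quartiles do not give it either.

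**The case against.** The case on the other side has several parts.

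- **The tests would be reported.** A reader might infer from Table 5-1 that key safety signals would not be tabulated. The documents do not support that. SAP 2.8.3 names AST, ALT, GGT and white cells with differential as data to be analysed, and commits to summaries, shift tables and flagged listings. This part of the objection stands.
- **Neutropenia is covered.** A reader might also infer that the neutrophil limit cannot be applied because no absolute count is displayed. That does not follow. SAP 5.4 sets limits for white cells (< 0.8 x LLN) and neutrophils (< 0.9 x LLN), differential counts are collected, and a list of displayed parameters does not prevent a derivation. What remains is only that the SAP does not say whether the limit applies to the percentage or to the absolute count.
- **Liver function has no special standing.** It would be too much to call it the protocol's main laboratory safety criterion. Protocol 10.2.1 and 10.2.2 report no liver or kidney signal and plan no special monitoring, and the endpoint for the safety objective is treatment-emergent adverse events. Protocol 12.5.2 describes no analysis of notable laboratory values. This limits the importance of the point but does not remove the mismatch, because Table 16-1 is itself captioned as serving safety analyses.
- **Some rows may be extraction losses.** A total white-cell row could have merged into its subgroup title, and absolute neutrophils would close their block. Those two omissions are not secure. Ten missing chemistry tests are harder to explain this way, and so is a criteria list written as running text.
- **The two lists may be complementary.** The protocol's limits are liver and renal, the SAP's are haematological, and section 4 declares no change. The sponsor may intend both to apply, and SAP section 1 leaves output details to shells that are not available here. That is possible, but the SAP does not say so and does not point to Table 16-1.

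**Conclusion.** The point holds as two documentation faults. First, SAP 5.4 contradicts SAP 2.8.3: a table said to be complete omits ten of 16 chemistry tests and total cholesterol, and shows no row for total white cells or absolute neutrophils in the text as read. Second, none of the five protocol limits for liver and renal tests has a counterpart in the SAP, so the planned notable-value summary would yield no count above any of them. Section 4 does not declare this departure.

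The effect is confined to safety reporting. Data collection and the efficacy analysis are untouched, and by-visit summaries and shift tables for these tests remain planned under SAP 2.8.3. The conclusion assumes that the notable-value summary uses the criteria printed in SAP 5.4 and that the unseen output shells do not already add the protocol's limits.

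**What to change.** 1. Make Table 5-1 match SAP 2.8.3. Add glucose, AST, ALT, GGT, sodium, potassium, bicarbonate, calcium, phosphorous, uric acid and total cholesterol. Confirm that rows for total white cells and absolute neutrophils are present, or add them. Adding only the liver enzymes and white-cell rows would leave the two sections in conflict.
2. State in SAP 5.4 that the neutrophil criterion applies to the absolute count.
3. Add the five protocol Table 16-1 limits to the notable criteria in SAP 5.4, and count patients meeting each by arm on the most extreme post-Baseline value, as SAP 2.1.2 already provides.

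The cost is a SAP text edit and a few output rows. The tests are already collected under protocol 8.4.4, so no new data are needed.
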